### **5.6.2 Secondary analysis**

All secondary endpoints at 72 weeks will be analyzed for the subgroup of patients who reach 72 weeks (or ICE). Analysis will be done for the full patient group until week 48, and a separate analysis will be done for the subgroup until week 72.

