#### Cognition

1. Proportion of subjects with a change of  $\geq 8$ ,  $\geq 4$ , and  $\geq 9$  for ALS Specific, ALS Non-Specific, and ECAS (Edinburgh Cognitive and behavioural ALS Screen) total score;
2. Change from baseline for ALS Specific, ALS Non-Specific, and ECAS total score at 24, 48 and 72\* weeks;

3. Time to a mean change of  $\geq 8$ ,  $\geq 4$ , and  $\geq 9$  for ALS Specific, ALS Non-Specific, and ECAS total score.

Pharmacokinetics

(Population) PK parameters of FAB122 and riluzole

\*All secondary endpoints at 72 weeks will be analyzed for the subgroup of patients that reach 72 weeks (or IE)

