## 2.4 Sample size

The sample size estimation is based on the primary endpoint: the change from baseline in ALSFRS-R score after 48 weeks. A difference of 3.0 points between FAB122 treatment arm and placebo is assumed with a (pooled) standard deviation of 7.5 and an allocation ratio of 2:1 (FAB122:Placebo). With these assumptions, a total sample size of 300 (200 patients on FAB122 and 100 on placebo) is needed to achieve 90% power to detect the difference of 3.0 points between the two treatment groups at a 5% (2-sided) level of significance.

For further details on the background of these assumptions, refer to the protocol.

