### 4.3 Secondary endpoint(s)

All secondary endpoints will be analyzed at 48 weeks including all patients, and additionally at 72 weeks for the subset of patients who reach 72 weeks (or ICE) as a subgroup analysis. The exception will be the planned main analysis for the key secondary endpoint of survival time (see below). This analysis will include data up to 48 weeks for all patients and up to 72 weeks for the subgroup of patients with planned extended follow-up. Analyses conducted at earlier time-points are informative but of lower relevance.

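### The general week-72 subgroup rule conflicts with the SAP's fixed 100-patient cohort and, as written, admits later-enrolled patients only through an intercurrent event

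*SAP*

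**What the plan says.** The general rule opens SAP 5.6.2: "All secondary endpoints at 72 weeks will be analyzed for the subgroup of patients who reach 72 weeks (or ICE". The bracket closes there and nothing restricts the group further. SAP 4.3 has every secondary endpoint analysed at week 48 in all patients and "additionally at 72 weeks for the subset of patients who reach 72 weeks (or ICE) as a subgroup analysis". The protocol carries the same rule as a footnote to the secondary endpoints in the synopsis, in 3.2.2 and in 11.3.4.3: "All secondary endpoints at 72 weeks will be analyzed for the subgroup of patients that reach 72 weeks (or IE".

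Other places describe a group fixed by design:

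- SAP 4.3, as an exception for the main survival-time analysis, uses data "up to 72 weeks for the subgroup of patients with planned extended follow-up".
- SAP 2.5, footnote 1 (and Protocol Table 1, footnote 1) has the first 100 patients continue to week 72 or an intercurrent event. Everyone else ends at week 48.
- SAP 5.2 says that only 100 patients are followed to week 72, and that the others' absent data between weeks 48 and 72 do not count as an intercurrent event.
- SAP 5.6.2 (week-72 RMST), 5.6.3 (joint model), 9.1 (CAFS ranking) and 10.3 (Topline output) each give the week-72 subgroup as 100 patients.

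**The concern.** The two rules select different patients. Take a patient randomised after the first 100. If free of intercurrent events at week 48, that patient stops there, has not reached week 72, and under SAP 5.2 has no intercurrent event, so is out. If that patient died or stopped treatment before week 48, an intercurrent event has been reached and the general rule lets the patient in. Membership among later patients therefore depends on what happened after randomisation.

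At stake is the validity of the week-72 results that rely on the general rule. Death and progression rates would be inflated. Because the protocol expects different discontinuation rates by arm, the selection could also differ between arms and produce an apparent treatment difference.

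**Working it through.** **The plan's own figure.** The documents give no week-72 event rate and no sample size for the week-72 subgroup. The one figure that can be reproduced is the overall sample size: "A difference of 3.0 points between FAB122 treatment arm and placebo is assumed with a (pooled) standard deviation of 7.5", for which 300 patients at 2:1 "is needed to achieve 90% power to detect the difference of 3.0 points" "at a 5% (2-sided) level of significance". Control-arm n = 1.5 × (1.960 + 1.282)² × (7.5/3.0)² = 98.5, rounded up to 99, or 297 in total. Power with 200:100 is 0.904. The stated figure reproduces, and the subgroup rule does not touch it.

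**Inputs for the illustration.**

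- First 100 patients followed to week 72, the other 200 to week 48 (SAP 2.5, footnote 1).
- Deaths by 52 weeks below 17% (SAP 5.2, Protocol 11.4). This is an upper bound, so I use r = 5%, 10% and 17%.
- Non-death intercurrent events from Protocol 11.4: discontinuation for adverse events about 7% FAB122 and 3% control, for lack of efficacy about 10% and 5%, and unrelated reasons at most 1%, taken as 1%. Sums: 18% FAB122, 9% placebo. No rate is given for rescue medication, so it is left out.
- Assumed, not in the documents: constant hazard, equal mortality in both arms, a 2:1 split within the first 100 and within the other 200, and the non-death rates applied to patients not dying by week 48.

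**Formulas.**

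- Deaths by week w: d(w) = 1 − (1 − r)^(w/52).
- Fixed cohort: d(72).
- Literal rule: (100 × d(72) + 200 × d(48)) / (100 + later patients with an intercurrent event).

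At r = 17%: d(48) = 15.8% and d(72) = 22.7%. With deaths as the only intercurrent event, 200 × 0.158 = 31.6 later patients join, giving (22.7 + 31.6)/131.6 = 54.3/131.6 = 41.3%.

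| Dead at 52 weeks | d(48) | Fixed 100, week 72 | Literal, deaths only | Literal, all intercurrent events |
|---|---|---|---|---|
| 5% | 4.6% | 6.9% | 16.1/109.2 = 14.7% | 16.1/137.9 = 11.7% |
| 10% | 9.3% | 13.6% | 32.1/118.5 = 27.1% | 32.1/145.8 = 22.0% |
| 17% | 15.8% | 22.7% | 54.3/131.6 = 41.3% | 54.3/156.9 = 34.6% |

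These are crude proportions. The literal rate is about 1.5 times (34.6/22.7) to 2.1 times (14.7/6.9) the fixed-cohort rate.

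**By arm, r = 17%, identical mortality, all intercurrent events.**

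- FAB122: later entrants 133.3 × (0.158 + 0.18 × 0.842) = 41.3; N = 66.7 + 41.3, about 107.9; deaths 66.7 × 0.2274 + 133.3 × 0.158 = 36.2; rate 33.6%.
- Placebo: later entrants 66.7 × (0.158 + 0.09 × 0.842) = 15.6; N = 33.3 + 15.6 = 48.9; deaths 33.3 × 0.2274 + 66.7 × 0.158 = 18.1; rate 37.0%.

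The gap of 3.4 points comes from selection alone.

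**Which outputs depend on the general rule.** The week-72 RMST, CAFS and joint model name the 100 patients themselves. In SAP 5.6.2, the paragraphs on time to ALSFRS-R change, overall survival, progression-free survival, staging, SVC, HHD, quality of life and cognition do not. The sentence in SAP 10.3 concerns outputs marked Topline. The tables for time to ALSFRS-R change, overall and progression-free survival, the staging Kaplan-Meier curves, SVC, HHD and quality of life are unmarked. For these, the general rule is the only definition.

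**The case against.** The strongest reply is that the intended group is visible. SAP 2.2 has the first third of randomised patients reach 72 weeks or an intercurrent event, and the phrase in 5.6.2 looks like shorthand for that clause. On that reading it keeps a first-100 patient whose follow-up was cut short by an event, which avoids survivor selection. SAP 5.2, 5.6.3, 9.1 and 10.3 all point to 100 patients, so the bias needs a programmer to follow the general rule and set those places aside. This stands as to intent and likelihood. It does not remove the conflict: SAP 4.3 puts both rules side by side and attaches the planned-follow-up wording only to the survival-time exception.

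A reader might also infer more than the documents support:

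- *Every week-72 estimate is biased.* No. SAP 4.3 exempts the main survival-time analysis, and three other analyses name the 100 patients. A later patient has no week-72 value, and SAP 5.6.2 applies no imputation to the other secondary endpoints, so week-72 descriptive changes are not reached directly. Only that patient's earlier visits could enter a repeated-measures model.
- *Later patients enter only if they fail.* Too strong. Intercurrent events in SAP 5.2 include rescue medication and unrelated reasons such as moving away. Entry depends on a post-randomisation event, not necessarily on failure.
- *Counting discontinuations makes the death rate worse.* The reverse. Discontinuers who are alive enlarge the denominator, and the rate at the 17% bound falls from 41.3% to 34.6%.
- *The confirmatory conclusions are at risk.* No. The week-48 primary and CAFS tests do not use this subgroup, and the survival-time step is covered by the exception. SAP 5.6 treats the endpoints outside the hierarchy as exploratory.

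**Conclusion.** The general definition is wrong as written, with low severity. It contradicts the fixed cohort used elsewhere in the SAP and, if programmed literally, selects later patients on a post-randomisation event. The exposure is mainly the exploratory week-72 time-to-event, overall survival, progression-free survival and staging analyses, and early-visit data in week-72 repeated-measures models.

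The size is conditional on the literal reading and on the assumptions listed in the working. It shows what the wording permits and does not predict what will be reported. The 17% is the documents' upper bound; the lower values are mine. The between-arm gap also depends on the protocol's expected discontinuation rates.

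**What to change.** In SAP 4.3 and 5.6.2, and in the protocol footnotes in the synopsis, 3.2.2 and 11.3.4.3, define the week-72 subgroup as the mITT patients among the first 100 randomised (planned 72-week follow-up), regardless of intercurrent events or discontinuation.

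The mITT restriction should be explicit because SAP 5.6 uses mITT for all secondary endpoints, while SAP 6 reports three mis-randomised patients who were never treated. If any of them is among the first 100, the subgroup is slightly smaller than 100.

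The cost is the same short edit in five places, made before unblinding. It needs no new data and does not change the sample size, the hierarchy or the week-48 analyses.

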#### Key secondary endpoints

No sensitivity analysis or intercurrent event correction will be applied for any of these key secondary endpoints.

#### **Combined assessment of function and survival (CAFS) at week 48 and 72**

CAFS is used to compare each study patient's outcome to others in the trial in a series of pairwise comparisons, based on function (i.e. ALSFRS-R score) and survival. See section 9.1 for relevant derivations. For each pairwise comparison, a study patient is assigned a score and then the summed scores are ranked for all patients.

Descriptive statistics for CAFS ranks will be made but are difficult to interpret as mean values depend on the size of the study. Descriptive statistics will also include mean difference in ranks with a 95% CI.

The difference between treatments CAFS ranks will be assessed using the Gehan-Wilcoxon rank test (also known as the Generalized Wilcoxon test) or, in case of relevant differences in baseline characteristics (as per factors included in the ANCOVA model mentioned), by using an ANCOVA model.

Regarding the Gehan-Wilcoxon rank test: if the analysis indicates a statistically significant effect, then the separate analysis of function and survival (as described below in the other secondary endpoints section) can provide insight whether the improved outcome for the group was driven by prolonged survival, improved function, or both. In case of an ANCOVA model: a General Linear Model (GLM) will be utilized with treatment, baseline ALSFRS-R score and stratification factors (slope of disease progression, concomitant use of riluzole) as covariates.

ALSFRS-R score values for patients who survived but have a missing week 48 score will be imputed following to the imputation defined in section 5.6.1, before the CAFS score will be

determined. The GLM will omit any (other) patients with missing data from the analysis. The duration from symptom onset is calculated from the medical history data.

In case of GLM, subsequent component analyses of function and survival will be used to determine which parameter(s) drive the overall effect on the CAFS results. The direction and magnitude of the function and survival components of the CAFS will inform the interpretation of the results.

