### **9.8. Unblinding**

This study will be performed in a double-blind fashion. The randomization list will not be available to the investigator, study staff, subjects, sponsor, or monitor. The investigational drug and its matching placebo are indistinguishable and will be packaged in the same way. Treatment emergency codes should not be broken except in emergency situations i.e., in case of a medical emergency or in the case a SUSAR occurs, the investigator or the sponsor's Unblinding Manager, will break the patient's code, through interactive web response system (IWRS), and if possible, the sponsor should be contacted before the emergency code is opened.

The investigator should only unblind the treatment allocation in the course of a clinical trial if this is relevant to the safety of the subject.

As regards the sponsor, when an event may be a SUSAR the blind should be broken by the sponsor only for that specific subject. The blind should be maintained for persons responsible for the ongoing conduct of the study (such as the management, monitors, investigators) and those responsible for data analysis and interpretation of results at the conclusion of the study, such as biometrics personnel. Unblinded information should only be accessible to those who need to be involved in the safety reporting to national competent authorities, Ethics Committees and Data Safety Monitoring Boards (DSMB), or persons performing ongoing safety evaluations during the trial.

---

It should be noted that unblinding is not necessarily a reason for patient's discontinuation and the patient could continue the study treatment and procedures after unblinding. Furthermore, patient's death will not be considered a systematic reason for unblinding and will only be performed if deemed necessary or requested by the IEC and/or CA.

The Unblinding Manager contact details are:  
[name] (Head of PV department, Pharmalex)  
[contact]  
Email: [contact]

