#### 11.3.4.3. Secondary Efficacy Endpoints

##### Key secondary endpoints

- Combined assessment of function and survival (CAFS) at 48 and 72 weeks
- Survival time, i.e. time to death, tracheostomy or initiation of non-invasive ventilation for more than 20 hours a day for more than 10 consecutive days, over 72 weeks

The CAFS will be used as key secondary endpoint as it combines information on survival and ALSFRS-R scores. For this endpoint, each patient's outcome will be ranked: the worst patient outcomes will receive the lowest rank numbers such that a higher CAFS score indicates a better outcome. The deceased cases will receive the lowest rank numbers followed by the level of decreases in ALSFRS-R scores. Descriptive statistics for this endpoint will be made but are difficult to interpret as mean values depend on the size of the study. In this study, with 300 patients the CAFS scores range from 1 to 300 with a total sum of 28,920 and an overall mean value of 120.5. The difference between treatments will be assessed using an ANCOVA model with the same covariates as the primary efficacy analysis. A rank-ANOVA will be used as a sensitivity analysis. Subsequent component analyses of function and survival will be used to determine which parameter(s) drive the overall effect on the CAFS results. The direction and magnitude of the function and survival components of the CAFS will inform the interpretation of the results.

'Survival', i.e. time to death, tracheostomy or initiation of non-invasive ventilation for more than 20 hours a day for more than 10 consecutive days, over 72 weeks Descriptive statistics (median and 25% and 75% quartiles with 95% confidence intervals) and Kaplan-Meier curves will be provided. The difference between oral FAB122 and placebo will be assessed using restricted mean survival time (RMST) analysis up to week 48 (and week 72), controlling for the stratification variables. In addition, also a Cox regression model and a stratified log-rank test will also be applied as sensitivity analysis, including factors for treatment and stratification variables.

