#### **3.3 Blind Data Review Meeting**

The patients will be classified during the (Blinded) Data Review Meeting (BDRM) to the analysis populations using the protocol deviations. Invitees to this meeting are the Sponsor Medical Representative (CTL or delegate), the Sponsor Project Manager (PM), the Sponsor PK scientist, Julius Clinical PM, Julius Clinical Data Manager (DM) and the Certara lead statistician, but more roles can be invited if considered necessary. Input to this meeting will be supplied by the involved Data Management Department or the responsible PM at least one week in advance of the meeting: a blinded list of all protocol deviations (including missing and outlier data), with specific detailing and description regarding the deviation, preferably in excel.

This meeting will be held in a blinded manner. The goal of this meeting is to reach consensus on minor and major protocol deviations. In case of a major deviation impacting the primary or secondary endpoints, the specific patient will be excluded from the PP population, either completely or from a specific time point onwards. The meeting must be held prior to database lock and unblinding.

The decisions taken during this meeting will be documented by the PM (or a delegate as agreed) and sent for review to all parties involved as soon as possible after the meeting, but before database lock. If all parties involved agree, then the document is finalized, signed and stored before database lock by the PM.

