## 4 STUDY ENDPOINTS

### 4.1 Hierarchical multiple testing

A hierarchical multiple testing procedure will be used to evaluate superiority of the primary endpoint, followed by the evaluation of superiority of the key secondary endpoints. A fixed sequence stepwise multiple testing procedure at the 0.05 level will be performed in the following pre-specified hierarchical order:

- I. Primary endpoint: change from baseline ALSFRS-R score after 48 weeks.
- II. Key secondary endpoint: CAFS at 48 weeks
- III. Key secondary endpoint: Survival time (death, tracheostomy or initiation of non-invasive ventilation for more than 20 hours a day for more than 10 consecutive days) over 72 weeks

Each step will be considered confirmatory if all previous steps were successful (i.e. if superiority was achieved). If any of the previous steps were unsuccessful, the subsequent steps are regarded as exploratory.

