### **5.6.1 Primary analysis**

The primary endpoint is defined as the change from baseline in total ALSFRS-R score after 48 weeks (primary timepoint).

For the primary analyses, a placebo (reference) multiple imputation (pMI) will be applied to impute missing data for any patients (i.e. from both treatment arms) who discontinue treatment early, irrespective the reason for drop-out (only when due to intercurrent events with unknown cause), and for which no data was collected after treatment discontinuation. The pMI method assumes the statistical behavior of placebo- and drug-treated patients after dropout is the statistical behavior of placebo-treated patients. A total of 20 imputed data sets will be created.

Before applying the statistical model to the primary endpoint, intercurrent events will be handled following the rules specified in Section 5.2.

The primary endpoint will be analyzed using a mixed model for repeated measures (MMRM), considering ALSFRS-R is assessed at multiple timepoints. The average treatment effect (lsmeans) and the treatment difference (estimand) of the change from baseline ALSFRS-R total score at 48 weeks will be extracted from the results from this model and presented together with the 95% confidence interval and p-value. Other timepoints will also be presented.

The model will include factors for treatment, time, treatment-by-time interaction, the stratification factor concomitant use of riluzole (yes/no), baseline ALSFRS-R score and the stratification factor slope of disease progression as fixed effects. An unstructured (UN) covariance matrix will be used in the model. If the model does not converge, the structure will be adapted to respectively AR(1), Toeplitz or Compound Symmetry (CS). The results of the 20 imputed data sets will be combined to obtain the final estimate of the treatment difference with 95% confidence interval and p-value.

An example SAS code which can be used as basis is as follows:

```
proc mixed data=<data>;
  class trt time riluse;
  model cfb=trt time trt*time riluse base disslope / ddfm=kr;
  repeated time/ subject=patient type=un;
  lsmeans trt*time/cl;
run;
```

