## 6 CHANGES FROM PROTOCOL AND OTHER RELEVANT REMARKS

The hybrid approach for missing data (Section 5.2) uses placebo-based pattern imputation under the MNAR assumption instead of last observation carried forward for patients who discontinued due to AE or lack of efficacy.

Several clarifications have been made to the sensitivity analyses.

A few minor typing errors have been corrected (e.g. creatine kinase instead of creatinine kinase)

For CAFS, the protocol states that “A rank-ANOVA will be used as a sensitivity analysis”. However, the CAFS are already ranked data and already analyzed via ANCOVA, so this specific analysis has been removed. Furthermore, it has been added that either a Gehan-Wilcoxon rank test or an ANCOVA or will be performed, based on assessment of baseline differences, as per literature reference. Lastly, for the analysis it is mentioned in the protocol that “the same covariates as the primary efficacy analysis” will be included. This is not completely true, as the time and time\*treatment interaction will not be included in the ANCOVA model, hence the variables are slightly different.

There are a few patients (# 3) that have been mis-randomized in the study and, consequently, did not receive study treatment. According to the definition, these patients still belong to the ITT population, being a secondary analysis population in this study. In principle no imputation will be applied for these patients for the primary endpoint and missingness is assumed to be MAR (missing at random). If the number of mis-randomized patients is larger than anticipated, a pMI approach will be considered for imputation of the baseline values.

There are several patients for who the CTCAE toxicity grade has been collected. These data will only be present in the CDISC files and the relevant listings, and not used in any descriptive statistics tabulations.

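### The confirmatory CAFS test at step II is unadjusted by default and moves to ANCOVA only on unquantified baseline differences; fix ANCOVA as the single test, whatever the balance

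*SAP*

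**What the plan says.** Protocol 11.3.4.3, key secondary endpoints: "The difference between treatments will be assessed using an ANCOVA model with the same covariates as the primary efficacy analysis". No condition is attached.

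SAP 5.6.2, CAFS: the difference in ranks "will be assessed using the Gehan-Wilcoxon rank test (also known as the Generalized Wilcoxon test) or, in case of relevant differences in baseline characteristics", by an ANCOVA model. The eligible characteristics are those in that model: baseline ALSFRS-R, slope of progression and riluzole use. In the same section, "Descriptive statistics will also include mean difference in ranks with a 95% CI"; this difference is unadjusted.

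SAP section 6 declares the change: "either a Gehan-Wilcoxon rank test or an ANCOVA or will be performed, based on assessment of baseline differences, as per literature reference". It also drops the protocol's rank-ANOVA, on the ground that the ranks are already analysed by ANCOVA.

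SAP 4.1 puts CAFS at 48 weeks at step II, between the primary endpoint and survival time: "Each step will be considered confirmatory if all previous steps were successful". SAP 5.6 calls the secondary analyses explorative but keeps this hierarchy.

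The neighbouring steps adjust unconditionally. The primary model (SAP 5.6.1) includes riluzole use, "baseline ALSFRS-R score and the stratification factor slope of disease progression as fixed effects". The survival-time RMST analysis (SAP 5.6.2) adjusts for the stratification variables.

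**The concern.** A confirmatory test should be known before treatment codes are opened. Here it depends on whether baseline differences between arms count as relevant, and nothing says how large a difference must be, who judges it, or when. Two statisticians could apply the sentence in good faith and run different step II tests on the same data.

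The default also sets aside covariates that the trial stratifies on and that the primary model uses. Section 6's reason for dropping the rank-ANOVA is true only if the switch occurs. The opening sentence on key secondary endpoints in SAP 5.6.2 plans no sensitivity analysis, so if the condition is not met there is no adjusted CAFS analysis at all. A missed step II also makes survival time exploratory.

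**Working it through.** **1. The plan's own figure.** Inputs (protocol 11.2, SAP 2.4): difference 3.0, SD 7.5, 2:1 allocation, two-sided 5%, 90% power.
- Placebo n = (1 + 1/2) × (1.960 + 1.282)² × (7.5/3.0)² = 98.5, so 99 and 297 in total; the plan states 300.
- At 200:100, SE = 7.5 × √(1/100 + 1/200) = 0.919; 3.0/0.919 = 3.266; power = Φ(3.266 − 1.960) = 90.4%.

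The figure reproduces. The documents give no power for CAFS.

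**2. Hand check of what adjustment is worth.** If covariates explain a share R² of the outcome variance, the standardised effect becomes 3.266/√(1 − R²). R² is not in the documents.

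| R² | Standardised effect | Power | Gain over 90.4% |
|---|---|---|---|
| 0.1 | 3.443 | 93.1% | 2.7 |
| 0.2 | 3.651 | 95.5% | 5.0 |
| 0.3 | 3.904 | 97.4% | 7.0 |

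This is for raw change scores without deaths. It overstates the loss, because stratified randomisation already helps the unadjusted test and some trials would switch to ANCOVA.

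**3. How often the switch would occur.** Stratification roughly balances slope stratum and riluzole, so the trigger is mainly baseline ALSFRS-R. Its standardised mean difference (SMD) has standard error √(1/100 + 1/200) = 0.1225.
- Trigger p<0.10: about 10% of trials (9.7–11.3% simulated).
- Trigger SMD >0.1: 2 × [1 − Φ(0.1/0.1225)] = 41% (about 40% simulated).

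Both are defensible readings of the same sentence.

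**4. Simulation on the CAFS scale.** N=300, 2:1, permuted blocks within four strata; riluzole 90% (protocol 8.3.1); survivor effect 3.0, SD 7.5. Assumed: 25% in the steep-slope stratum, R² 0.1–0.3, and death risk sharing the covariates and half the residual variance. Deaths (placebo/FAB122) were set at none, 10/9% or 17/15%; the documents expect under 17% at 52 weeks. Power at R² 0.2:

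| Deaths | Rule at p<0.10 | ANCOVA always | Loss |
|---|---|---|---|
| none | 90.9% | 94.1% | 3.2 |
| 10/9% | 82.6% | 88.1% | 5.5 |
| 17/15% | 76.9% | 83.0% | 6.1 |

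- A repeat simulation gave losses of 2.9 (91.6 v 94.5%), 4.5 (86.5 v 91.0%) and 8.0 (75.4 v 83.4%).
- Over R² 0.1–0.3, the p<0.10 rule loses 1.6–5.1 points without deaths and 2.2–11.3 with deaths. SMD >0.1 loses about 1.0, 2.0 and 2.8 points without deaths at R² 0.1, 0.2 and 0.3. The extremes over five triggers tried were 0.7 and 12.3.
- Chance of reaching step III at R² 0.2, rule v ANCOVA: 82.2 v 87.5% (10/9%) and 76.5 v 82.6% (17/15%).
- The two tests disagree on significance at R² 0.2 in 3.7–6.3% of trials without deaths and 6.2–12.9% with deaths.

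**5. Sensitivity to the death model.** With 12% deaths and a different death model, Wilcoxon always against ANCOVA always gave 85.3 v 86.3%, 85.9 v 89.8% and 86.9 v 93.9% at R² 0.05, 0.15 and 0.30: losses of 1.0, 3.9 and 7.0.

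**6. Type I error.** Fixed balance rules: 2.5–4.7%. ANCOVA always, in the 12% deaths model: 5.0–5.4%, with simulation error of about 0.3 points.

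**The case against.** The change is declared in SAP section 6 with a literature reference, and the eligible factors are named. That stands: this is an open choice, not a hidden contradiction, and what is undefined is the threshold, the decision-maker and the timing.

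The power loss rests on an assumed R² and death model. That also stands. The upper figures need strong covariates and deaths near the bound the documents expect not to reach; with 12% deaths and another death model, the largest loss was 7 points. The larger losses are not peculiar to one run, since the repeat at 17/15% deaths lost 8.0 points at R² 0.2.

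Three stronger readings are tempting.

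- **The switch inflates the confirmatory error rate.** The calculations do not support this. A fixed rule is conservative. Picking the smaller p-value freely gives an ungated 5.1–6.8%, but step II counts only after a significant primary. With the primary significant in FAB122's favour, the rate was 1.9% under the global null (17% deaths, R² 0.2). It was 2.1–2.6% when a real survivor benefit is cancelled within CAFS, which needs FAB122 deaths of 25–35% against 5–17% on placebo.
- **The SAP plans to choose after unblinding.** It gives no date. The trigger compares arms, while of the planned data review the SAP says "This meeting will be held in a blinded manner", and the protocol says "The randomization list will not be available to the investigator, study staff, subjects, sponsor, or monitor". That the choice needs treatment codes is therefore an inference.
- **Nearly all trials would stay on the weaker test.** About 90% follows from a p<0.10 trigger, which the SAP does not state; under SMD >0.1 it is about 60%.

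**Conclusion.** The concern holds as a matter of efficiency and of an unsettled confirmatory test. Step II is the only step in the hierarchy that ignores the stratification factors by default, and its switch to adjustment cannot be reproduced from the text.

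The expected cost against ANCOVA always is roughly 1–5 points of power without deaths and 1–11 points with 10–17% deaths, for R² 0.1–0.3. It is smaller under a loose trigger and nil at R² 0. At R² 0.2 the choice of test would change the step II result in about 4–13% of trials. The direction and the ambiguity are secure. The exact sizes are not, because R², the death model and the trigger are all assumed. The primary analysis is unaffected. This should be fixed, but it does not threaten the trial's validity.

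**What to change.** Before unblinding, amend the SAP:

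1. **5.6.2, CAFS, and section 6:** delete the condition. Make ANCOVA on the CAFS ranks the single confirmatory test regardless of baseline balance, with treatment, baseline ALSFRS-R, riluzole stratum and slope.
2. **Slope coding:** state that slope enters as the randomisation stratum (<1.0 v ≥1.0). Pointing to the primary model does not settle this: SAP 5.6.1 calls slope a stratification factor, but its example code leaves the variable out of the CLASS statement.
3. **Imputation:** state that the ANCOVA treatment estimate is pooled over the 20 imputed data sets by Rubin's rules. The CAFS section borrows the imputation of 5.6.1 without saying how results are combined.
4. **Gehan-Wilcoxon:** report it as supportive, and reword the opening sentence on key secondary endpoints in 5.6.2 to allow this. The survival section already includes supportive tests.

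The cost is wording in these SAP places. The model and covariates are already listed, no new data are needed, and the protocol's choice of ANCOVA is restored.

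Separately, protocol 11.3.4.3 needs a clerical correction that affects no test. For 300 patients the rank sum is 300 × 301/2 = 45,150 and the mean 150.5; the printed 28,920 and 120.5 belong to 240 patients (240 × 241/2).
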